9.2.4. Investigation Classification per European Regulation 2017/745

According to European Regulation 2017/745, RGnCON is a clinical investigation conducted to establish the conformity of a non-CE marked non-invasive class IIa medical device, referred to in Articles 62 and 70.7 a) of the Regulation (case 1 per the French National Competent Authority (ANSM) classification).

9.3. Benefits and Risks of the Investigational Device, Clinical Procedure and Clinical Investigation

9.3.1. Anticipated Clinical Benefits

The potential clinical benefits anticipated to result from the use of RGn550 in patients with acute concussion syndrome are:

- Improvement of automated oculomotor / oculopostural functions,
- Improvement of balance function,
- Improvement of executive function,
- Decrease of concussion syndrome symptoms
- Reduction of neuroinflammation.

These potential benefits are investigated in RGnCON.

9.3.2. Anticipated Adverse Device Effects

The following Adverse Device Effects (ADEs) were observed during the pilot investigation on RGn530 (previous version of the device) and are thus considered as anticipated ADEs of RGn550:

[REDACTED]

Per RGn550's investigator brochure, the ADEs anticipated to result from the use of RGn550 are:

[REDACTED]

| | | |
|--------|---|--|
| RGnCON | Clinical Investigation Plan Version 2.0 - 11 August 2022 | |
|--------|---|--|

[REDACTED]
[REDACTED]
No severe ADEs are expected.

9.3.3. Risks Associated with the Participation in the Clinical Investigation

Compared to standard clinical practice, additional risks associated with the participation in RGnCON are risks related to:

- **The use of RGn550**

Anticipated ADEs of RGn550 are described above (section 9.3.2).

Moreover, as mentioned in RGn550's investigator brochure, a risk management process specific to RGn550 was put in place by REGEnLIFE in accordance with NF EN ISO 14971-2019.

- **The automated oculomotor/oculopostural tests and the TMT A & B**

Identified risks related to the conduct of such tests are symptoms such as fatigue, headache and dizziness, which are related to the fact that treated patients have a concussion. These symptoms remain acceptable as they are usual symptoms of concussions, expected to remain minor within this context.

- **The stabilometric test**

The only risk that has been identified as related to the use of the stabilometry platform is a risk of stumble/fall of the patient. However, this risk remains very unlikely considering the reduced height of the platform and the fact that investigators, which are healthcare professionals, will help and support patients during the whole stabilometric process.

- **The blood sampling procedure**

Risks related to the blood sampling procedure are pain, hematoma at the puncture site, lack of blood reflux, reflex syncope as well as contamination by hepatitis C, C or HIV for the person performing the sampling. These risks are mitigated by the fact that a nurse will be perform the sampling.

No risks were identified as being related to the use of the Sport Concussion Assessment Tool – 5th edition (SCAT5) symptom evaluation tool.

9.3.4. Possible Interactions with Concomitant Treatments

As mentioned in the IFU, RGn550 should not be used in:

- Patients with recent major surgery at the treatment application area (head) within 3 months
- Patients with ferromagnetic material
- Patient with a pacemaker.

No interactions with pharmacological treatments are mentioned in the IFU.

9.3.5. Steps Taken to Control or Mitigate Risks and Benefit-Risk Ratio Rationale

All risks identified during RGn550's risk analysis were mitigated as far as possible. It was concluded that anticipated benefits outweigh residual risks and the overall residual risk is acceptable.

| | |
|---|--------------|
| 2022.08.11_RGnCON_Proto_Final_V2.0_clean_public | Page 32 / 82 |
|---|--------------|

| | | |
|--------|---|---|
| RGnCON | Clinical Investigation Plan Version 2.0 - 11 August 2022 |  |
|--------|---|---|

Risks related to investigation procedures mentioned in section 9.3.3 are mitigated by the fact that healthcare professionals will help and support patients during the whole investigation. Investigators will conduct all evaluations while a nurse will perform the blood sampling.

A risk analysis specific to RGnCON will be put in place. This risk analysis will take into consideration any risks associated with each step of the investigation. Associated documentation will describe all steps taken to control and mitigate these risks.

| | |
|--|--------------|
| 2022.08.11_RGnCON_Prot_Final_V2.0_clean_public | Page 33 / 82 |
|--|--------------|

| | | |
|--------|---|---|
| RGnCON | Clinical Investigation Plan Version 2.0 - 11 August 2022 |  |
|--------|---|---|

9.4. Clinical Investigation Objectives and Hypotheses

As a pilot investigation, the objective of RGnCON is to demonstrate RGn550's safety and explore its performance in treating adult sportspeople with acute concussion syndrome.

9.4.1. Primary Objective

The primary objective of this investigation is to evaluate the **incidence of RGn550's ADEs** in acute concussion syndrome, when used to deliver, either at a frequency of 5 or 10 Hz, two 20-min treatment sessions at 1 week apart.

9.4.2. Secondary Objectives

The secondary objectives of this investigation relate to both the **safety** and **performance** of RGn550 in acute concussion syndrome, when used to deliver, either at a frequency of 5 Hz or 10 Hz, two 20-min treatment sessions at 1 week apart.

These objectives are:

- To evaluate the **incidence of RGn550's ADEs per severity, AEs and Device Deficiencies (DDs)**
- To evaluate the effect of RGn550, after the first and second treatment sessions and then 45 days after the second treatment session, on:
 - **Automated oculomotor and oculopostural functions**
 - **Balance function**
 - **Executive function**
- To assess the effect of RGn550 on **concussion syndrome symptoms** 7 days after the first treatment session as well as 7 and 45 days after the second treatment session.
- To evaluate the effect of RGn550 on **blood markers** that are involved in the pathogenesis of concussion 45 days after the second treatment session.

These secondary objectives have been chosen as they will allow to evaluate RGn550's safety and determine whether:

- RGn550 could improve important functions that are impacted in acute concussion syndrome, i.e., automated oculomotor/oculopostural, balance and executive functions
- RGn550 could decrease acute concussion syndrome symptoms
- RGn550 could impact the concentration of blood markers involved in acute concussion syndrome

| | | |
|--------|---|---|
| RGnCON | Clinical Investigation Plan Version 2.0 - 11 August 2022 |  |
|--------|---|---|

9.5. Clinical Investigation Design

9.5.1. Investigational Medical Devices

Two RGn550 devices producing a 5 Hz frequency and two producing a 10 Hz frequency will be provided by REGEnLIFE to the investigational site. Provided devices will be tracked, during and after the investigation, with assigned serial numbers.

The principal investigator will be trained in the use of RGn550 by REGEnLIFE before the inclusion of the first patient.

Each patient will be treated with the same device throughout the investigation. For a given patient, the other device of the same type (5 Hz or 10 Hz) may only be used in case of malfunction of the initial device.

To maintain simple blinding, the devices will be visually identified as follows:

- The RGn550 devices producing a 5 Hz frequency will be labeled as: Device A1 and Device A2
- The RGn550 device producing a 10 Hz frequency will be labeled as: Device B1 and Device B2.

To track the use of the devices, the principal investigator will mention in the electronic Case Report Form (eCRF) which RGn550 device was used at each treatment session of each patient. In parallel, he will fulfil a treatment sheet associated with the device in question and write down the number of the treated patient, date of treatment, number of treatment session and duration of treatment.

The maximal overall exposure of patients to RGn550 will be of 1 week, since the second, and last, treatment session is planned at Day 7. Exposure during a treatment session will be of 20 min.

9.5.2. Investigation Population

Adult sportspeople with acute concussion syndrome resulting from sport practice who can participate in a clinical investigation per the law and are able to meet treatment sessions and complete requested assessments will be included.

9.5.2.1. Inclusion Criteria

- Male or female aged at least 18 years old
- Suffering from concussion syndrome resulting from a shock that occurred during sport practice less than 72h ago, as confirmed by neurological examination via the Head Injury Assessment - Form 3 (HIA3) tool
- Affiliated to French social security
- Who provided a dated and signed informed consent form.

9.5.2.2. Non-Inclusion Criteria

- Patient protected by a French legal measure ("sauvegarde de justice", "tutelle" or "curatelle")
- Patient not able to express his/her consent
- Patient deprived of liberty or hospitalized without consent
- Woman who is pregnant or breastfeeding, or who plans to become pregnant or breastfeeding during the investigation, or who has the capacity to conceive but is not using a reliable contraceptive method as deemed by the investigator
- Patient living in a medical facility

| | | |
|--------|---|---|
| RGnCON | Clinical Investigation Plan Version 2.0 - 11 August 2022 |  |
|--------|---|---|

- Patient who experienced a surgery at the treatment application area (head) within 3 months prior to inclusion
- Patient with skin lesions on the treatment application area (head)
- Patient with a short-term life-threatening pathology (e.g., evolving cancer; non-stable heart failure; severe hepatic, renal or respiratory failure, etc.)
- Patient diagnosed with a heart attack within 3 months prior to inclusion
- Patient implanted with ferromagnetic material
- Patient implanted with a pacemaker
- Patient with a risk of epileptic seizure or other non-degenerative central nervous system diseases
- Patient with major physical or neurosensorial disorders that may interfere with assessments
- Patient with chronic psychosis or psychotic episodes
- Patient addicted to alcohol or drugs
- Patient treated with antidepressant or benzodiazepine
- Patient who participated to another investigation/study involving the use of an investigational medical device/drug within the 30 days prior inclusion
- Patient not able to meet treatment sessions as deemed by the investigator
- Patient not able to complete requested investigation assessments as deemed by the investigator.

9.5.3. Conduct

9.5.3.1. Patient Inclusion

It is planned to include 50 patients in this investigation (refer to section 9.6.1 for sample size justification).

Based on this number and considering that the site estimated that it would be able to include approximately 3 patients per week, a 4-month inclusion period is planned: from September 2022 to December 2022.

The recruited site will be the Hôpital européen Georges-Pompidou located in Paris. The principal investigator will be a neurologist specialized in sport concussions and the coinvestigator will be a sport physician and posturologist.

In current clinical practice, following a shock, a sportsperson with obvious signs of concussion is examined by a physician within 72 hours after the shock to establish the diagnosis of concussion. For example, in the context of professional rugby, the French federation's regulation requires to follow HIA protocol immediately after the shock and the appearance of such signs. This protocol, composed of three steps, is performed by a physician within 48 hours after the shock:

- Step 1: Assessment during the match using HIA1
- Step 2: Post-match assessment, the same day, using HIA2
- Step 3: 36-48 hours post-injury assessment using HIA3.

The subjects of RGnCON investigation will be identified among sportspersons examined by the principal investigator within 72 hours after the shock. They will be included if they meet eligibility criteria and agree to participate in the investigation. Of note, HIA3 is mentioned in the eligibility criteria as the diagnostic tool for concussion. Indeed, as the principal investigator is the referring neurologist for a lot of rugby clubs and several sports federations, it is expected that most subjects will be professional rugby players for whom this protocol is implemented in current clinical practice. Nevertheless, subjects practicing other sports may be included as well if they have a diagnosis of concussion confirmed by the HIA3, meet the eligibility criteria and agree to participate.

All potential subjects will be informed about the investigation as soon as possible after the shock in order to give them adequate time to think about the investigation and their potential participation. During the consultation with the principal investigator, all the information will be reexplained to the patients, who will then be able to ask the investigator any questions they may have. After that, patients will have as much time as needed to provide an answer regarding their participation. If the answer is provided within 72 hours after the shock, then the patient will be included.

9.5.3.2. Visits

Three onsite visits will be performed at the following timepoints:

- Day 0 (D0): Inclusion, randomization (to the 5 Hz or 10Hz treatment group) and first treatment session
- Day 7 (D7): Second treatment session
- Day 52 (D52): Evaluation 45 days after the last treatment session.

In addition, at Day 14 (D14), the patient will be asked to remotely assess his/her concussion syndrome symptoms.

9.5.3.3. Investigation Duration

The investigation duration per subject will be of 52 days.

The overall investigation duration, which corresponds to the inclusion period and the follow-up period, will thus be of 6 months approximately (4 months of inclusion and 52 days of follow-up).

9.5.3.4. Prohibited/Restricted Treatments

Other treatments involving **PBM** or **magnetic fields** will be prohibited during the investigation in order to evaluate RGn550's effects only.

The following pharmacological treatments will be prohibited as well as during the investigation in order to evaluate RGn550's effects only: **benzodiazepine** and **antidepressants**.

In addition, any patients who have a **head surgery** or get implanted with **ferromagnetic material** or a **pacemaker** between the first and second RGn550 treatment sessions will not undergo the second treatment session because RGn550 is contraindicated in these conditions.

Of note, the same will apply to patients who meet **other contraindications** between the two treatment sessions, i.e.:

- Patients with skin lesions on the head
- Patients with short-term life-threatening pathologies (e.g., evolving cancer, non-stable heart failure, severe hepatic, renal or respiratory failure, etc.)
- Patients with a heart attack
- Patients with a risk of epileptic seizure
- Pregnant women.

9.5.3.5. End of Investigation

The end of the investigation is defined as the completion of the last patient last visit. The last patient last visit will occur when the last patient either completes the 52-day follow-up visit or prematurely terminate the investigation.

A patient may prematurely terminate the investigation for the following reasons:

- Screen failure

| | | |
|--------|---|---|
| RGnCON | Clinical Investigation Plan Version 2.0 - 11 August 2022 |  |
|--------|---|---|

- Withdrawal
- Lost to follow-up
- Death.

For each patient, an end-of-investigation form will be filled in within the eCRF by the investigator, whether or not they have completed the investigation. In case of premature termination, the date and reason will be collected.

Screen failure

A screen failure occurs when a patient was included while he/she has one or several non-inclusion criteria and/or does not have one or several inclusion criteria.

In that case, the investigators must ensure that the reason for screen failure is adequately documented in the patient's medical file and the eCRF.

Withdrawal

Patients may voluntarily withdraw from the investigation at any time. A patient may also be withdrawn from the investigation at the investigators' discretion.

In case of withdrawal, the investigators must ensure that the date and reason for the withdrawal is adequately documented in the patient's medical file and the eCRF.

Data from all patients who left the investigation prematurely will be analyzed until the date of withdrawal.

Lost to Follow-Up

When investigators do not have any news from a patient, they will make at least three attempts to contact the patient as well as the patient's general practitioner and/or a family member if known. If all these attempts fail, the investigators can then declare the patient as "lost to follow-up". In that case, every effort will be made to obtain necessary information to complete the eCRF.

Each attempt should be documented in the patient's medical file with the date, description of the three unsuccessful contacts along with the contact method (e.g., telephone, letter with acknowledgement of receipt).

Of note, to prevent lost-of follow-up patients, automatic alerts will be sent via emails to the site to remind them of upcoming visits with their patients.

Data from patients who were lost to follow-up will be analyzed until the date of loss to follow-up.

Death

Should it be discovered that the patient is dead, an investigation regarding the cause of death will be conducted by the investigator. The date and cause of death will be recorded in the eCRF and the patient's medical file.

Data from dead patients will be analyzed until the date of death.

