9.5.5.3. Remote Visit (D14)

Seven days after the second treatment session, the investigators will **call the patients** to remind them to complete the SCAT5 symptom evaluation tool and bring the form with them during their next visit at D52.

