9.5.5.4. Follow-up Visit (D52)

During this visit, which will occur 45 days after the second treatment session, no treatment will be performed.

The investigators will:

- Collect the **SCAT5 symptom evaluation tool form** that was completed by the patient at D14
- **Collect any AEs** that occurred since the last visit
- **Check** that, between the first and second treatment sessions, patients did not have a **second concussion**. If that's the case, remaining performance evaluations won't be performed.
- If applicable, **perform the following tests**:
 - NPC
 - Cover test
 - Maddox rod test
 - Static stabilometric test

The patient will be asked to evaluate the intensity of his/her symptoms using the SCAT5 symptom evaluation tool.

Finally, a **blood sample** will be obtained by the nurse.

Once all these evaluations have been conducted and all the required data have been collected, a treatment session may be offered to patients who did not become **contraindicated** to RGn550 treatment after the second treatment session.

Patients who became contraindicated to RGn550 treatment or had a second concussion between the first and second treatment session will not come on site for this visit since no further performance evaluations will be performed for these patients. However, the principal investigator will call them on D52 to collect any AEs that occurred since the last visit.

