9.5.5.5. Schedule

Table 2 below summarizes procedures and evaluations to perform at each visit.

| | |
|--|--------------|
| 2022.08.11_RGnCON_Prot_Final_V2.0_clean_public | Page 45 / 82 |
|--|--------------|

| | | |
|--------|---|---|
| RGnCON | Clinical Investigation Plan Version 2.0 - 11 August 2022 |  |
|--------|---|---|

Table 2: Schedule of procedures and evaluations

| | D0 | | D7 | | D14 (remote) | D52 |
|--|------------------|-----------------|------------------|-----------------|-----------------|-----|
| | Before treatment | After treatment | Before treatment | After treatment | | |
| Patient information / Informed consent | X | | | | | |
| Eligibility criteria | X | | | | | |
| Pregnancy test for women of childbearing potential | X | | | | | |
| Randomization | X | | | | | |
| Demographic and clinical data | X | | | | | |
| NPC | X | X | X | X | | X |
| Cover test | X | X | X | X | | X |
| Maddox rod test | X | X | X | X | | X |
| Stabilometric test | X | X | X | X | | X |
| TMT A&B | X | | | X | | |
| SCAT5 symptom evaluation tool | X | | X | | X | X |
| Blood sampling | X | | | | | X |
| 20-min treatment session | X | | X | | | |
| Collection of AEs and DDs that previously occurred | | X | X | X | | X |

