9.13.3. Safety Reporting to Sponsor

Per Article 80 of the European Regulation 2017/745, the following events shall be recorded:

- Any AE of a type identified in the CIP as being critical to the evaluation of the results of that clinical investigation
- Any SAEs
- Any DD that might have led to a SAE if appropriate action had not been taken intervention had not occurred, or circumstances had been less fortunate
- Any new findings in relation to the above events.

The following events that occur in patients included in RGnCON from inclusion to the end of the 52-day follow-up period will thus be recorded:

- All AEs, including SAEs
- All DDs
- Any new findings in relation to AEs and DDs.

AEs will be reported using the Adverse Event form of the eCRF while DDs will be reported using the Device Deficiency form. The date of the event, its severity, causality, treatment and resolution will notably be collected.

These events will be reported immediately to REGEnLIFE and no later than 3 calendar days after the investigator becomes aware of the event.

If needed, the investigations site team or [REDACTED] can contact REGEnLIFE's materiovigilance department via email ([contact]) or phone ([contact]).

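### Patients who withdraw have no scheduled adverse-event collection after their last attended visit, although the primary endpoint runs to D52; the cut-at-withdrawal sentence should be limited to performance data.

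*Protocol*

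**What the plan says.** **Endpoint and recording window.** Protocol 9.5.4.1 sets the primary endpoint as ADE incidence over the whole investigation, which is 52 days per subject (9.5.3.3). Protocol 9.13.3 says that events in included patients "from inclusion to the end of the 52-day follow-up period will thus be recorded", and its list ends with "Any new findings in relation to AEs and DDs".

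**Scheduled collection.** The row "Collection of AEs and DDs that previously occurred" in Table 2 (Protocol 9.5.5.5) is marked after treatment at D0, before and after treatment at D7, and at D52. At D14 the investigators call patients "to remind them to complete the SCAT5 symptom evaluation tool and bring the form with them during their next visit at D52"; no AE question is mentioned. For patients who became contraindicated or had a second concussion between the sessions, 9.5.5.4 replaces the D52 visit by telephone: "However, the principal investigator will call them on D52 to collect any AEs that occurred since the last visit". Other early leavers are not included in that call.

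**Early leavers.** Protocol 9.5.3.5 states: "Data from all patients who left the investigation prematurely will be analyzed until the date of withdrawal". For the end-of-investigation form it adds: "In case of premature termination, the date and reason will be collected".

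**SAP.** Sections 8.4.2 and 8.4.3 use all AEs held in the eCRF, with no cut at withdrawal. The exclusion of later data in 8.5.1 concerns performance endpoints and a switch of treatment group. Section 8.4.1 reports 0% loss to follow-up at data review. No number of withdrawals is given.

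**The concern.** The recording rule in 9.13.3 works only if the investigator learns of the event. While a patient stays in the trial, the D52 visit guarantees that someone asks. Once a patient withdraws, nothing in the schedule does, even if that patient would be willing to take a call. For someone who leaves between D7 and D52, the D52 question that is lost would also have covered the days between D7 and the departure.

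The sentence on analysis in 9.5.3.5 makes no exception for safety data. If an ADE dated after withdrawal did reach the eCRF, a reader applying that sentence literally would leave it out, while a reader applying SAP 8.4.2 would keep it.

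Both routes lead towards fewer ADEs. The SAP's primary variable is a yes/no for at least one ADE, and no rule treats an early leaver as missing, so a patient with no recorded ADE would presumably count as a no. Withdrawal may also be linked to harm: 9.5.3.5 lets investigators withdraw patients at their discretion, and the template in SAP 8.1 lists an adverse event among the reasons.

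**Working it through.** **The plan's own figure.** Inputs from Protocol 9.6.1: N = 50, ADE probability 0.04. The chance of at least one ADE is 1 − 0.96^50 = 0.8701, which matches the stated 0.87. It is not in dispute.

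**Length of the gap.** A patient who leaves after D7 was last asked about AEs on D7. The remainder is 52 − 7 = 45 days, and 45/52 = 86.5% of follow-up. This is calendar time, not a share of risk.

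**Effect of one missed event.** The plan implies 0.04 × 50 = 2 expected patients with an ADE. With exact Clopper-Pearson limits:

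- 2/50 = 4.0% (95% CI 0.5 to 13.7)
- 1/50 = 2.0% (95% CI 0.1 to 10.6)

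**Chance of missing at least one first ADE.** The documents supply only the 4%. The rest is assumed:

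- w patients leave ADE-free (1, 3 or 5 of 50);
- a share f of the 4% risk falls after their last AE collection;
- leaving is unrelated to risk;
- no later event comes to light by another route.

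For a patient who is ADE-free at the last collection, the risk still to come is q = 0.04f / (1 − 0.04(1 − f)). The chance of at least one missed is 1 − (1 − q)^w.

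| f | q | w = 1 | w = 3 | w = 5 |
|---|---|---|---|---|
| 0.10 | 0.0041 | 0.4% | 1.2% | 2.1% |
| 0.25 | 0.0103 | 1.0% | 3.1% | 5.0% |
| 0.50 | 0.0204 | 2.0% | 6.0% | 9.8% |
| 1.00 | 0.0400 | 4.0% | 11.5% | 18.5% |

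The last row is a ceiling. It puts no ADE risk at all during or just after treatment, which is implausible here because "the second, and last, treatment session is planned at Day 7" and Protocol 9.5.5.1 and 9.5.5.2 collect AEs straight after each session. If leaving is linked to harm, the figures could be higher than shown.

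**The case against.** A reader might infer that protocol and SAP contradict each other, and that ADEs after withdrawal will be struck from the primary analysis. The documents do not support that, for three reasons.

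- Protocol 9.6.3 leaves full statistical detail to the SAP, and the SAP keeps all AEs in the eCRF. Its own exclusion of later data is confined to performance endpoints.
- The withdrawal sentence is one of three parallel lines in 9.5.3.5; the others concern loss to follow-up and death. A patient who has died has no later AEs to cut, so the three together read most naturally as saying that data up to exit are kept.
- Protocol 9.13.3 governs recording and 9.5.3.5 governs analysis, so those two do not collide directly.

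Nor does the sentence about date and reason mean that AEs of leavers go unrecorded. It describes the end-of-investigation form, and AEs have their own eCRF form.

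On size, establishing why a patient left normally requires contact, so an AE that caused the departure would usually be known and recordable. Completers also go 45 days between scheduled AE collections. What a withdrawn patient loses is one retrospective question at D52. The endpoint is descriptive, with no test or success threshold.

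All of this stands, and it limits the point to a wording ambiguity plus a narrow gap in collection. It does not close the gap: outside the D52 call for two groups, no planned contact asks an early leaver about AEs. The reported 0% loss to follow-up does not settle it either, because SAP 8.1 lists loss to follow-up separately from consent withdrawal and other reasons.

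**Conclusion.** The gap in scheduled collection is real, and it bears on a primary endpoint defined over the full 52 days. The sentence in 9.5.3.5 is loosely worded, but the SAP's rule on AEs makes a safety cut unlikely to have been intended.

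Any error is towards fewer ADEs. It is probably small, and it may be nil if few or no treated patients withdrew. It cannot be sized from the documents because they give no withdrawal count; the range of 0.4% to 9.8% for f from 0.10 to 0.50 rests wholly on the assumptions listed with it. A reading that the primary result is materially biased would go beyond what the documents show. The point is a cheap improvement of minor severity.

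**What to change.** 1. In Protocol 9.5.5.4, extend the existing D52 AE call to every treated patient who leaves early and does not refuse contact. The call already asks about the time since the last visit, so it also covers the days between that visit and the departure.
2. In Protocol 9.5.3.5, limit the cut at withdrawal to performance data, and say that AEs and device deficiencies are handled under 9.13.3 and the SAP's safety sections.

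SAP 8.4.2 and 8.4.3 need no change, since they already use all AEs in the eCRF.

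The cost is two protocol sentences and a few extra telephone calls of a kind the principal investigator already makes. If data collection is over, as the planned last visit in February 2023 and the SAP date of August 2023 suggest, only the wording can change, and events that were never collected will not be recovered.
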